12.4 Response Criteria for Patients with Solid Tumor and Measurable Disease

12.4.1 Evaluation of Target Lesions

Complete Response (CR):	Disappearance of all target and non-target lesions. Any pathological lymph nodes (whether target or non-target) must have reduction in short axis to <10 mm. If immunocytology is available, no disease must be detected by that methodology. Normalization of urinary catecholamines or other tumor markers if elevated at study enrollment (for patients with neuroblastoma).
Partial Response (PR):	At least a 30% decrease in the sum of the diameters of target lesions, taking as reference the baseline sum diameters
Progressive Disease (PD):	At least a 20% increase in the sum of the diameters of target lesions, taking as reference the smallest sum on study (this includes the baseline sum if that is the smallest on study). In addition to the relative increase of 20%, the sum must also demonstrate an absolute increase of at least 5 mm. (Note: the appearance of one or more new lesions

is also considered progressions). Note: in presence of SD or PR in target disease but unequivocal progression in non-target or non-measurable disease, the patient has PD if there is an overall level of substantial worsening in non-target disease such that the overall tumor burden has increased sufficiently to merit discontinuation of therapy

Stable Disease (SD):

Neither sufficient shrinkage to qualify for PR nor sufficient increase to qualify for PD, taking as reference the smallest sum diameters while on study

12.4.2 Evaluation of Non-Target Lesions

Complete Response (CR):

Disappearance of all non-target lesions and normalization of tumor marker level. All lymph nodes must be non-pathological in size (<10 mm short axis)

Note: If tumor markers are initially above the upper normal limit, they must normalize for a patient to be considered in complete clinical response.

Non-CR/Non-PD:

Persistence of one or more non-target lesion(s) and/or maintenance of tumor marker level above the normal limits

Progressive Disease (PD):

Appearance of one or more new lesions and/or *unequivocal progression* of existing non-target lesions. *Unequivocal progression* should not normally trump target lesion status. It must be representative of overall disease status change, not a single lesion increase.

12.4.3 Overall Response Assessment

Table 1: For Patients with Measurable Disease (i.e., Target Disease)

Target Lesions	Non-Target Lesions	New Lesions	Overall Response	Best Overall Response when Confirmation is Required*
CR	CR	No	CR	≥ 28 days Confirmation
CR	Non-CR/Non-PD	No	PR	≥ 28 days Confirmation
CR	Not evaluated	No	PR	
PR	Non-CR/Non-PD/not evaluated	No	PR	
SD	Non-	No	SD	documented at least once ≥

	CR/Non-PD/not evaluated			28 days from baseline
PD	Any	Yes or No	PD	no prior SD, PR or CR
Any	PD**	Yes or No	PD	
Any	Any	Yes	PD	
* See RECIST 1.1 manuscript for further details on what is evidence of a new lesion.				
** In exceptional circumstances, unequivocal progression in non-target lesions may be accepted as disease progression.				
Note: Patients with a global deterioration of health status requiring discontinuation of treatment without objective evidence of disease progression at that time should be reported as “ symptomatic deterioration. ” Every effort should be made to document the objective progression even after discontinuation of treatment.				

Table 2: For Patients with Non-Measurable Disease (i.e., Non-Target Disease)

Non-Target Lesions	New Lesions	Overall Response
CR	No	CR
Non-CR/non-PD	No	Non-CR/non-PD*
Not all evaluated	No	not evaluated
Unequivocal PD	Yes or No	PD
Any	Yes	PD

* ‘Non-CR/non-PD’ is preferred over ‘stable disease’ for non-target disease since SD is increasingly used as an endpoint for assessment of efficacy in some trials so to assign this category when no lesions can be measured is not advised
		

Table 3: Overall Response for Patients with Neuroblastoma and Measurable Disease

CT/MRI	MIBG	Bone Scan	Bone Marrow	Catechol	Overall
PD	Any	Any	Any	Any	PD
Any	PD	Any	Any	Any	PD
Any	Any	PD	Any	Any	PD
Any	Any	Any	PD	Any	PD
SD	CR/PR/SD	Non-PD	Non-PD	Any	SD
PR	CR/PR	Non-PD	Non-PD	Any	PR
CR/PR	PR	Non-PD	Non-PD	Any	PR
CR	CR	Non-PD	Non-PD	Elevated	PR
CR	CR	CR	CR	Normal	CR

12.4.4 Overall Best Response Assessment

Each patient will be classified according to his “best response” for the purposes of analysis of treatment effect. Best response is determined as outlined in [Section 12.9](#) from a sequence of overall response assessments.

12.5 Response Criteria for Neuroblastoma Patients with MIBG Positive Lesions

12.5.1 MIBG Positive Lesions

Patients who have a positive MIBG scan at the start of therapy will be evaluable for MIBG response. The use of ^{123}I for MIBG imaging is recommended for all scans. If the patient has only one MIBG positive lesion and that lesion was radiated, a biopsy must be done at least 28 days after radiation was completed and must show viable neuroblastoma.

12.5.2 The following criteria will be used to report MIBG response by the treating institution:

Complete response: Complete resolution of all MIBG positive lesions

Partial Response: Resolution of at least one MIBG positive lesion, with persistence of other MIBG positive lesions

Stable disease: No change in MIBG scan in number of positive lesions

Progressive disease: Development of new MIBG positive lesions

[figure not shown]
12.5.3 The response of MIBG lesions will be assessed on central review using the Curie scale¹⁴ as outlined below. Central review responses will be used to assess efficacy for study endpoint. See [Section 8.2](#) for details on transferring images to the Imaging Research Center.

NOTE: This scoring should also be done by the treating institution for end of course response assessments.

The body is divided into 9 anatomic sectors for osteomedullary lesions, with a 10th general sector allocated for any extra-osseous lesion visible on MIBG scan. In each region, the lesions are scored as follows. The **absolute extension score** is graded as:

- 0 = no site per segment,
- 1 = 1 site per segment,
- 2 = more than one site per segment,
- 3 = massive involvement (>50% of the segment).

The **absolute score** is obtained by adding the score of all the segments. See diagram of sectors below:

The **relative score** is calculated by dividing the absolute score at each time point by the corresponding pre-treatment absolute score. The relative score of each patient is calculated at each response assessment compared to baseline and

classified as below:

1. **Complete response:** all areas of uptake on MIBG scan completely resolved. If morphological evidence of tumor cells in bone marrow biopsy or aspiration is present at enrollment, no tumor cells can be detected by routine morphology on two subsequent bilateral bone marrow aspirates and biopsies done at least 21 days apart to be considered a **Complete Response**.
2. **Partial response:** Relative score ≤ 0.2 (lesions almost disappeared) to ≤ 0.5 (lesions strongly reduced).
3. **Stable disease:** Relative score > 0.5 (lesions weakly but significantly reduced) to 1.0 (lesions not reduced).
4. **Progressive disease:** New lesions on MIBG scan.

12.5.4 Overall Response Assessment

Table 4: Overall Response Evaluation for Neuroblastoma Patients and MIBG Positive Disease Only

If patients are enrolled without disease measurable by CT/MRI, any new or newly identified lesion by CT/MRI that occurs during therapy would be considered progressive disease.

MIBG	CT/MRI	Bone Scan	Bone Marrow	Catechol	Overall
PD	Any	Any	Any	Any	PD
Any	New Lesion	Any	Any	Any	PD
Any	Any	PD	Any	Any	PD
Any	Any	Any	PD	Any	PD
SD	No New Lesion	Non-PD	Non-PD	Any	SD
PR	No New Lesion	Non-PD	Non-PD	Any	PR
CR	No New Lesion	Non-PD	Non-PD	Elevated	PR
CR	No New Lesion	CR	CR	Normal	CR

12.5.5 Overall Best Response Assessment

Each patient will be classified according to his “best response” for the purposes of analysis of treatment effect. Best response is determined from the sequence of the overall response assessments as described in [Section 12.9](#).

12.6 Response Criteria for Neuroblastoma Patients with Bone Marrow Involvement

12.6.1 Bone Marrow Involvement

Note: patients with bone marrow as the ONLY site of disease are not eligible for this study. Response criteria in this section are intended to be used when assessing marrow involvement as a component of overall response.

Histologic analysis at the local institution of marrow tumor cell involvement is **required** for patients with a history of marrow involvement. Marrow aspirate and biopsy should be evaluated at baseline and every 2 cycles thereafter. Note: If progressive disease is documented by RECIST criteria using tumor measurements or by MIBG scan, then a repeat BM is not needed to confirm PD.

Complete Response: No tumor cells detectable by routine morphology on 2 consecutive bilateral bone marrow aspirates and biopsies

performed at least 21 days apart. Normalization of urinary catecholamines or other tumor markers if elevated at study enrollment.

Progressive Disease: In patients who enroll with neuroblastoma in bone marrow by morphology have progressive disease if there is a doubling in the amount of tumor in the marrow AND a minimum of 25% tumor in bone marrow by morphology. (For example, a patient entering with 5% tumor in marrow by morphology must increase to $\geq 25\%$ tumor to have progressive disease; a patient entering with 30% tumor must increase to $> 60\%$).

In patients who enroll without evidence of neuroblastoma in bone marrow will be defined as progressive disease if tumor is detected in 2 consecutive bone marrow biopsies or aspirations done at least 21 days apart.

Stable Disease: Persistence of tumor in bone marrow that does not meet the criteria for either complete response or progressive disease.

12.6.2 Overall Best Response Assessment

Each patient will be classified according to his “best response” for the purposes of analysis of treatment effect. Best response is determined from the sequence of the overall response assessments as described in [Section 12.9](#).

12.7 **Response Criteria for Patients with CNS Tumors**

12.7.1 Measurable Disease

Any lesion that is at minimum 10 mm in one dimension on standard MRI or CT, for CNS tumors.

12.7.2 Evaluable Disease

Evaluable disease is defined as at least one lesion, with no lesion that can be accurately measured in at least one dimension. Such lesions may be evaluable by nuclear medicine techniques, immunocytochemistry techniques, tumor markers, CSF cytology, or other reliable measures.

12.7.3 Selection of Target and Non-Target Lesions

For most CNS tumors, only one lesion/mass is present and therefore is considered a “target” for measurement/follow up to assess for tumor progression/response. If multiple measurable lesions are present, up to 5 should be selected as “target” lesions. Target lesions should be selected on the basis of size and suitability for accurate repeated measurements. All other lesions will be followed as non-target lesions. The lower size limit of the target lesion(s) should be at least twice the thickness of the slices showing the tumor to decrease the partial volume effect (e.g., 8 mm lesion for a 4 mm slice).

Any change in size of non-target lesions should be noted, though does not need to be measured.

12.7.4 Response Criteria for Target Lesions

Response criteria are assessed based on the product of the longest diameter and its longest perpendicular diameter. Development of new disease or progression in any established lesions is considered progressive disease, regardless of response in other lesions – e.g., when multiple lesions show opposite responses, the progressive disease takes precedence. Response Criteria for target lesions:

- **Complete Response (CR):** Disappearance of all target lesions. Off all steroids with stable or improving neurologic examination.
- **Partial response (PR):** $\geq 50\%$ decrease in the sum of the products of the two perpendicular diameters of all target lesions (up to 5), taking as reference the initial baseline measurements; on a stable or decreasing dose of steroids with a stable or improving neurologic examination.
- **Stable Disease (SD):** Neither sufficient decrease in the sum of the products of the two perpendicular diameters of all target lesions to qualify for PR, nor sufficient increase in a single target lesion to qualify for PD; on a stable or decreasing dose of steroids with a stable or improving neurologic examination.
- **Progressive Disease (PD):** 25% or more increase in the sum of the products of the perpendicular diameters of the target lesions, taking as reference the smallest sum of the products observed since the start of treatment, or the appearance of one or more new lesions.

Increasing doses of corticosteroids required to maintain stable neurological status should be strongly considered as a sign of clinical progression unless in the context of recent wean or transient neurologic change due e.g. to radiation effects.

12.7.5 Response Criteria for Non-Target Lesions:

- **Complete Response (CR):** Disappearance of all non-target lesions.
- **Incomplete Response/Stable Disease (IR/SD):** The persistence of one or more non-target lesions.
- **Progressive Disease (PD):** The appearance of one or more new lesions and/or unequivocal progression of existing non-target lesions.

12.7.6 Response criteria for tumor markers (if available):

Tumor markers will be classified simply as being at normal levels or at abnormally high levels.

12.7.7 Overall Response Assessment

The overall response assessment takes into account response in both target and non-target lesions, the appearance of new lesions and normalization of markers (where applicable), according to the criteria described in the table below. The

overall response assessment is shown in the last column, and depends on the assessments of target, non-target, marker and new lesions in the preceding columns.

Target Lesions	Non-target Lesions	Markers	New Lesions	Overall Response
CR	CR	Normal	No	CR
CR	IR/SD	Normal	No	PR
CR	CR, IR/SD	Abnormal	No	PR
PR	CR, IR/SD	Any	No	PR
SD	CR, IR/SD	Any	No	SD
PD	Any	Any	Yes or No	PD
Any	PD	Any	Yes or No	PD
Any	Any	Any	Yes	PD

Each patient will be classified according to his “best response” for the purposes of analysis of treatment effect. Best response is determined as outlined in [Section 12.9](#) from a sequence of overall response assessments.

12.8 Response Criteria for Patients with non-Hodgkin Lymphoma/Histiocytosis

Response and progression will be evaluated in this study using the new international criteria proposed by the revised Response Evaluation Criteria in Pediatric non-Hodgkin Lymphoma Criteria¹⁰, with modification from the Lugano classification.¹¹

12.8.1 Disease Parameters

12.8.1.1 Measurable disease: A measurable node must have an LD_i (longest diameter) greater than 1.5 cm. A measurable extranodal lesion should have an LD_i greater than 1.0 cm. All tumor measurements must be recorded in millimeters (or decimal fractions of centimeters).

12.8.1.2 Non-measured disease: All other lesions (including nodal, extranodal, and assessable disease) should be followed as nonmeasured disease (e.g., cutaneous, GI, bone, spleen, liver, kidneys, pleural or pericardial effusions, ascites).

12.8.1.3 Target lesions: For patients staged with CT, up to six of the largest target nodes, nodal masses, or other lymphomatous lesions that are measurable in two diameters (longest diameter [LD_i] and shortest diameter) should be identified from different body regions representative of the patient's overall disease burden and include mediastinal and retroperitoneal disease, if involved.

12.8.2 Evaluation of Measurable Disease

Complete Response (CR)

Disappearance of all disease. CT or MRI should be free of residual mass or evidence of new disease. FDG-PET should be negative.

Complete Response Unconfirmed (CRu)

Residual mass is negative by FDG-PET; no new lesions by imaging examination; no new and/or progressive disease elsewhere

Partial Response (PR)

50% decrease in SPD (the sum of the products of the largest diameter and the perpendicular diameter for a tumor mass) on CT or MRI; FDG-PET may be positive (Deauville score of 4 or 5 with reduced lesional uptake compared with baseline); no new and/or PD; morphologic evidence of disease may be present in BM if present at diagnosis; however, there should be 50% reduction in percentage of lymphoma cells.

No Response (Stable Disease)

Neither sufficient shrinkage to qualify for PR nor sufficient increase to qualify for PD, taking as reference the smallest sum diameters while on study.

Progressive disease

For those with > 25% increase in SPD on CT or MRI, Deauville score 4 or 5 on FDG-PET with increase in lesional uptake from baseline, or development of new morphologic evidence of disease in BM

12.8.3 Evaluation of Non-measured Lesions (CT-based response, PET/CT based response not applicable)¹¹

Complete Response (CR): Absent non-measured lesions.

Partial response (PR): Absent/normal, regressed, lesions, but no increase.

Stable Disease (SD): No increase consistent with progression

Progressive Disease (PD): New or clear progression of preexisting non-measured lesions.

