This subprotocol is a component of the NCI-COG Pediatric MATCH trial APEC1621. The APEC1621SC screening protocol details the assay used for the integral genomic profiling which will determine eligibility for this subprotocol. Here we will conduct a phase 2 trial of tazemetostat in children with recurrent or refractory solid tumors (including non-Hodgkin lymphomas, histiocytoses and CNS tumors) harboring specified activating genetic alterations in EZH2 or members of the SWI/SNF complex. EPZ-6438 (tazemetostat) is a selective small molecule inhibitor of the histone methyltransferase EZH2.¹ Tazemetostat will be administered orally twice daily at the recommended phase 2 dose (RP2D) as determined by the ongoing pediatric phase 1 trial. The primary endpoint will be objective response rate as determined by RECIST. Progression-free survival (PFS) will be assessed as a secondary endpoint.

EXPERIMENTAL DESIGN SCHEMA

For patient(s) enrolled Pre-amendment #3B:

Day 1-28	Day 28
Tazemetostat 1200 mg/m ² /dose (Orally, twice daily)	Evaluation

For patient(s) enrolled post-amendment #3B:

	Day 1-28	Day 28
Patients without CNS involvement	Tazemetostat 520mg/m ² /dose (Orally, twice daily)	Evaluation
Patients with CNS involvement	Tazemetostat 1200 mg/m ² /dose (Orally, twice daily)	Evaluation

Tazemetostat will be administered orally twice daily (based on disease location per above table); a cycle will be 28 days.

Tumor evaluations will occur at the end of every other cycle x 3, then every 3 cycles.

Therapy will be discontinued if there is evidence of progressive disease or drug related dose-limiting toxicity that requires removal from therapy ([Section 6.0](#)). Therapy may otherwise continue for up to 2 years (maximum of 26 cycles) provided the patient meets the criteria for starting subsequent cycles ([Section 5.2](#)) and does not meet any of the criteria for removal from protocol therapy criteria ([Section 10.0](#)).

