 - 3 If patients develop Grade 3 or greater thrombocytopenia then CBCs should be checked every 3 to 4 days until recovery to Grade 3, per [Section 6.1](#).
 - 4 Tumor Disease Evaluation should be obtained on the next consecutive cycle after initial documentation of either a PR or CR. Subsequent scans may restart 2 cycles after the confirmatory scan. Please note that for solid tumor patients, if the institutional investigator determines that the patient has progressed based on clinical or laboratory evidence, he/she may opt not to confirm this finding radiographically.
 - 4-A Neurological exam also required for CNS patients.
 - 4-B Non- Hodgkin Lymphoma/ Histiocytosis patients are required to have PET scans within 2 weeks prior to start of therapy and should also be followed with PET scans if positive at diagnosis. Refer to [Section 12.8](#).
 - 4-C Patients with neuroblastoma must have both CT/MRI and MIBG scintigraphy prior to enrollment if the patient was enrolled with or has a history of having MIBG avid tumor. Otherwise the patient must have both CT/MRI and bone scan prior to enrollment. For patients with neuroblastoma and measurable disease by CT or MRI, lesions should be measured and followed using the same modality (CT or MRI) in addition to MIBG or bone scan. For patients with neuroblastoma and evaluable disease by MIBG scintigraphy or bone scan, use the same modality (MIBG scintigraphy or bone scan) to image and follow patients; CT/MRI are not required but may be performed as clinically indicated. Refer to [Section 12.5.4](#) and [Section 12.9](#).
 - 5 Bone marrow aspirate and/or biopsy only required in patients suspected of having bone marrow metastasis on the basis of history, symptoms, laboratory evaluation or other clinical data. Should only be performed on patients with known bone marrow involvement at baseline.
 - 6 Bone marrow aspirate and/or biopsy should be performed only when complete response or partial response is identified in target disease or when progression in bone marrow is suspected.
 - 7 Patient diary (see [Appendix III](#)) should be reviewed weekly during Cycle 1 and then after completion of each treatment cycle and uploaded into RAVE.

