8.3 Radiology Studies

8.3.1 Bone Age/Knee MRI

All tibial radiographs and knee MRIs (if obtained) should be submitted for review.

8.3.2 Central Radiology Review for Response:

Patients who respond (CR, PR) to therapy or have long term stable disease (SD) (≥ 6 cycles) on protocol therapy will be centrally reviewed. The Operations center will notify the site when a patient has met the criteria for review. The tumor disease evaluations to be submitted for review include baseline (pre-study) evaluations as well as all end of cycle tumor disease evaluations which occurred while the patient was on the subprotocol therapy study..

8.3.3 Technical Details of Submission:

To ensure an adequate interpretation of FDG-PET and CT with contrast scans, scans transferred between the treating institutions and the Imaging and Radiation Oncology Core Group IROC RI (QARC) must be submitted in Digital Imaging and Communications in Medicine (DICOM) format. BMP files, JPG files, or hard copies (films) are unacceptable for adequate interpretation of PET and CT with contrast scans. Imaging studies must be submitted electronically as outlined in the following paragraph. The images will be made available to study radiologists and nuclear medicine physicians for central review.

Submission of Diagnostic Imaging data in DICOM format is required.

Submission of the digital files and reports via TRIAD is preferred. Instructions for TRIAD set up are below.

Alternatively, the images and reports may be submitted via sFTP to IROC Rhode Island. Digital data submission instructions including instructions for obtaining a sFTP account, can be found at <http://irocri.qarc.org>. Follow the link labeled digital data. Sites using the Dicomcommunicator software to submit imaging may continue to use that application.

Corresponding Radiology reports may be submitted along with the electronic submission via TRIAD or sFTP or may be emailed to [contact]. The COG operations center and IROC are available to assist with any queries regarding the corresponding radiology reports which should be included when the scans are submitted

Questions may be directed to [contact] or [contact].

Digital RT Data Submission Using TRIAD (if TRIAD is available at your site):
TRIAD is the American College of Radiology's (ACR) image exchange

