- 12.3.3.6 Cytology, Histology: These techniques can be used to differentiate between partial responses (PR) and complete responses (CR) in rare cases (e.g., residual lesions in tumor types, such as germ cell tumors, where known residual benign tumors can remain).

Cytology should be obtained if an effusion appears or worsens during treatment when the measurable tumor has met criteria for response or stable disease.

12.3.3.7 **FDG-PET:** While FDG-PET response assessments need additional study, it is sometimes reasonable to incorporate the use of FDG-PET scanning to complement CT scanning in assessment of progression (particularly possible 'new' disease). New lesions on the basis of FDG-PET imaging can be identified according to the following algorithm:

- a. Negative FDG-PET at baseline, with a positive FDG-PET at follow-up is a sign of PD based on a new lesion.
- b. No FDG-PET at baseline and a positive FDG-PET at follow-up: If the positive FDG-PET at follow-up corresponds to a new site of disease confirmed by CT, this is PD. If the positive FDG-PET at follow-up is not confirmed as a new site of disease on CT, additional follow-up CT scans are needed to determine if there is truly progression occurring at that site (if so, the date of PD will be the date of the initial abnormal FDG-PET scan). If the positive FDG-PET at follow-up corresponds to a pre-existing site of disease on CT that is not progressing on the basis of the anatomic images, this is not PD.

Note: A 'positive' FDG-PET scan lesion means one that is FDG avid with an uptake greater than twice that of the surrounding tissue on the attenuation corrected image.

For patients with a positive PET scan at diagnosis, PET can be used to follow response in addition to a CT scan using the International Pediatric non-Hodgkin Lymphoma Response Criteria.¹⁰

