12.8.4 Evaluation of organ enlargement¹¹

Complete Response (CR): Regress to normal

Partial response (PR): Spleen must have regressed by >50% in length beyond normal

Stable Disease (SD): No increase consistent with progression

Progressive Disease (PD): In the setting of splenomegaly, the splenic length must increase by 50% of the extent of its prior increase beyond baseline. If no prior splenomegaly, must increase by at least 2 cm from baseline.

New or recurrent splenomegaly

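### The lymphoma partial-response rule ties residual marrow disease to diagnosis instead of study entry, and the related marrow, PET and spleen reference points are misdirected or undefined

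*Combined protocol and SAP*

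**What the plan says.** The abstract describes the population as "children with recurrent or refractory solid tumors (including non-Hodgkin lymphomas, histiocytoses and CNS tumors", treated after earlier disease.

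**Marrow.** In Section 12.8.2, the PR definition states that "morphologic evidence of disease may be present in BM if present at diagnosis; however, there should be 50% reduction in percentage of lymphoma cells". It does not say from when the 50% is measured. In the same definition, PET uptake is compared with baseline. Progression includes "development of new morphologic evidence of disease in BM", again without a reference time.

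**PET.** Footnote 4-B to the table in Section 8.1 requires a PET within two weeks before therapy in all lymphoma and histiocytosis patients. It then says that they "should also be followed with PET scans if positive at diagnosis". Section 12.3.3.7 has similar wording: "For patients with a positive PET scan at diagnosis, PET can be used to follow response in addition to a CT scan".

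**Spleen.** In Section 12.8.4, the PR line is "Spleen must have regressed by >50% in length beyond normal". The progression line is "In the setting of splenomegaly, the splenic length must increase by 50% of the extent of its prior increase beyond baseline".

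Section 12.8 defines neither *at diagnosis* nor *baseline*. Section 8.3.2 uses baseline in the sense of pre-study when it lists the evaluations sent for central review, which "include baseline (pre-study) evaluations as well as all end of cycle tumor disease evaluations".

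**The concern.** In newly diagnosed disease, diagnosis and study baseline are the same moment. In a relapsed population they can be years apart, and marrow or PET status may differ between them. A rule that looks back to diagnosis then judges the study drug against a state that it did not start from.

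Responder status feeds the primary endpoint, where success turns on 3 responses among 20 patients (Section 11.3.1), so a single patient can matter. Later steps may not catch the error. Routine central review covers patients who respond or have stable disease for at least 6 cycles (Section 8.3.2), so a child scored locally as a non-responder for a shorter time may not be reviewed.

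**Working it through.** **1. Reference times side by side**

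| Rule | Reference time |
|---|---|
| 12.8.2 PR: residual marrow disease tolerated | diagnosis |
| 12.8.2 PR: 50% fall in marrow involvement | not stated |
| 12.8.2 PD: new marrow disease | not stated |
| 12.8.2 PR and PD: PET uptake | baseline |
| 8.1 footnote 5: who has marrow examined | involvement at baseline |
| 12.6.1: neuroblastoma marrow progression | enrollment |
| 4.0: timing of pre-study marrow, when applicable | within 14 days before therapy |
| 8.1 footnote 4-B and 12.3.3.7: PET follow-up | diagnosis |
| 12.8.4 PR: spleen | normal |
| 12.8.4 PD: enlarged spleen | baseline, undefined |

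Diagnosis is the outlier among the marrow rules. A study-entry marrow exists whenever marrow is examined.

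**2. Marrow, lost responder (assumed values).** Marrow is 0% at diagnosis, 40% at entry and 15% on treatment, and SPD is down 60%. The marrow fall from entry is (40 − 15)/40 = 62.5%. Both falls exceed 50%, yet the remaining marrow disease was not present at diagnosis, so the literal text refuses PR. A fall measured from 0% at diagnosis is not even defined.

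**3. Marrow, unstated reference for the 50% (assumed values).** Marrow is 80% at diagnosis, 30% at entry and 35% on treatment. From diagnosis the fall is (80 − 35)/80 = 56%, so the marrow condition is met. From entry, involvement rose by 5 percentage points, so it is not met. The other PR conditions would still have to hold.

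**4. PET.** Uptake for PR and PD is already compared with baseline. Only the trigger for follow-up looks back to diagnosis. A child who is PET-positive at entry but was negative or not scanned at diagnosis has no required follow-up PET, although CR and CRu both call for a negative PET.

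**5. Spleen (assumed lengths: normal 10 cm, entry 14 cm).** The PR limit is 10 + 0.5 × (14 − 10) = 12 cm. If baseline in the PD line means normal length, the PD limit is 14 + 0.5 × (14 − 10) = 16 cm. If it means the pre-study scan, the prior increase at entry is 14 − 14 = 0 and the limit is 14 + 0.5 × 0 = 14 cm. The text does not choose between the two.

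**6. Size.** Inputs from Section 11.3: N = 20, success at 3 or more responses, rates 5% and 25%, stated alpha 10% and power 90%.

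- Reproduced by exact binomial: P(X ≥ 3 | 20, 0.05) = 0.0755, which is under the 10% ceiling, and P(X ≥ 3 | 20, 0.25) = 0.9087.
- Let k of the 20 be lymphoma or histiocytosis patients, and let a share f of their true responders be scored as non-responders. Then power = P(A + B ≥ 3), with A ~ Bin(20 − k, 0.25) and B ~ Bin(k, 0.25 × (1 − f)). Both k and f are assumptions.

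| k | f = 25% | f = 50% | f = 100% |
|---|---|---|---|
| 1 | 0.9037 | 0.8987 | 0.8887 |
| 2 | 0.8985 | 0.8877 | 0.8647 |
| 4 | 0.8872 | 0.8625 | 0.8029 |

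The last column is an outer limit. It assumes that every responder in this group has the marrow pattern in step 2.

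**The case against.** The reference to diagnosis may be loose wording for study entry, since marrow work-up elsewhere is keyed to baseline. A sensible assessor might read it so. But the same definition uses baseline for PET, so a reader has reason to think that the two words differ. The marrow pattern is also narrow: clear at diagnosis, involved at entry, residual on treatment, with SPD halved. That is fair and limits the size.

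Four stronger readings are tempting, and the documents do not support them.

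- *Marrow that was 40% at diagnosis, clear at entry and 10% on treatment could pass as PR.* The PR definition also requires no new or progressive disease. Marrow disease appearing on study after a clear entry marrow is, on the natural reading, new. No inflation of the false-positive rate can be built on this case.
- *The child in step 2 would be scored as progressed.* That needs new to mean new since diagnosis, which is not stated. The literal consequence is a lost PR.
- *PET response is scored against diagnosis.* It is not. Section 12.3.3.7 is permissive, and neither passage bars PET in other children. PR can be met on SPD by CT or MRI with a positive PET, so no loss to the response rate is shown from PET alone.
- *Any growth of an enlarged spleen is progression.* The wording presupposes a non-zero prior increase, which fits excess over normal. The stable-disease line in 12.8.4 implies that some increases are not progression. Section 8.3.2 says which evaluations go to central review and does not define the spleen reference.

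**Conclusion.** The marrow condition for PR is wrong as written for a relapsed population: it can deny PR to a child who responds on study. The references for the 50% marrow fall and for new marrow disease are missing, and the first gap could credit marrow disease that rose on study if diagnosis is taken as the reference. For PET, the defect is confined to who is followed. For the spleen, the progression line is undefined and inconsistent with the response line; a zero threshold is one possible reading and is not established.

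The effect on power depends on two quantities that the documents do not give. Under the stated assumptions it runs from about half a percentage point (0.909 to 0.904: one patient, 25% missed) to about 11 points (0.909 to 0.803: four patients, all missed). The design itself reproduces and needs no change.

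**What to change.** - **12.8.2, PR:** make residual marrow disease acceptable *if present at the pre-treatment baseline evaluation*, and measure the 50% marrow reduction from that evaluation.
- **12.8.2, PD:** define new marrow disease as disease absent at that baseline.
- **8.1 footnote 4-B and 12.3.3.7:** use the same pre-treatment reference for PET follow-up, so that the scans needed to score CR and CRu exist.
- **12.8.4, PD:** reconcile the spleen reference with the PR line, which uses excess over normal length.

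The cost is wording in a few places, plus follow-up PET for any child who is positive at entry but was not at diagnosis. Sample size, decision rule and analysis method stay as they are.
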